## 4.2 Scientific rationale for study design

The clinical efficacy, safety, and tolerability of ZLP 0.3mg/kg/day administered SC has been evaluated over 12 weeks in both MG0009 and MG0010. These studies demonstrated a statistically significant and clinically meaningful benefit of ZLP treatment on efficacy measures and a favorable safety and tolerability profile over placebo (Section 2.3). MG0017 is an open-label, single-arm study to evaluate the safety, tolerability, and efficacy of ZLP in study participants with gMG switching from their current IV C5 inhibitor to SC ZLP. The open-label, single-arm design without the inclusion of a placebo control is acceptable for this study since SC ZLP has already been shown to be numerically superior to the efficacy observed with the approved IV C5 inhibitors eculizumab and ravulizumab (Section 2.3), and it also allows all study participants to continue to receive an effective treatment (as opposed to an inert control). The 12-week treatment duration of the Main Treatment Period in this study was chosen as it is consistent with the pivotal Phase 3 study (MG0010). In the MG0010 study, a rapid separation of efficacy between ZLP and placebo was observed after 1 week which was maximized within 4 weeks and was then maintained through the course of the 12-week study. The rationale for dose selection in this study is provided in Section 4.3. The Extension Treatment Period was added to provide access to ZLP for participants with gMG who have completed the Main Treatment Period and who wish to continue receiving ZLP.

The study population will include adults with gMG who have been receiving an IV C5 inhibitor approved for the treatment of gMG for at least 3 months (for eculizumab) or 4 months (for ravulizumab) prior to Screening with a clinically stable disease as per the Investigator's judgment. Only study participants who are willing to switch from their current IV C5 inhibitor to SC ZLP will be included in the study. There is no minimum number of study participants switching from either eculizumab or ravulizumab in this study in order to keep with real world clinical practice for the treatment of patients with gMG.

## 4.3 Justification for dose

is thereof.

#### **4.4 End of study definition**

##### **Completion of main treatment period for the participant**

A participant is considered to have completed the **Main Treatment Period** if he/she completed the Week 12 visit and:

- Decided to enter the Extension Treatment Period.

OR

- Transitioned to commercially available ZLP directly after the Week 12 visit (no Withdrawal or SFU visit required).

OR

- Decided not to enter the Extension Treatment Period and completed a SFU visit.

##### **Completion of study for the participant**

A participant is considered to have **completed the study** if he/she completed the Main Treatment Period and:

- Did not enter the Extension Treatment Period.

OR

- Entered the Extension Treatment Period and:

- withdrew from the Extension Treatment Period, discontinued ZLP, and completed the Withdrawal and SFU Visits.

OR

- transitioned to commercially available ZLP and completed the Withdrawal Visit. No SFU Visit is required.

## End of study

The end of the study is defined as the date of the last visit of the last participant in the study.

## 5 STUDY POPULATION

Prospective approval of protocol deviations to recruitment and enrollment criteria, also known as protocol waivers or exemptions, is not permitted.

### 5.1 Inclusion criteria

Participants are eligible to be included in the study only if all of the following criteria apply:

#### Age

1. Participant must be between 18 years and 85 years of age, inclusive, at the time of signing the Informed Consent form (ICF).

#### Type of participant and disease characteristics

- 2a. Participant has been treated with an IV C5 inhibitor approved for the treatment of gMG at the recommended dose regimen for at least 3 months (for eculizumab) or 4 months (for ravulizumab) prior to Screening with a clinically stable disease as per the Investigator's judgment.

NOTE: The last dose of the IV C5 inhibitor must be taken at the Screening Visit ( $\pm 3$  days) (Section 4.1). Participant is willing to switch from his/her current IV C5 inhibitor to SC ZLP.

4. Participant has a documented diagnosis of gMG (MGFA Class II-IVa) at Screening based on participant history and supported by previous evaluations.

5. Participant has a well-documented record of positive serology for acetylcholine receptor binding autoantibodies prior to Screening.

6. Participant has no more than a 2-point change in MG-ADL score at Baseline compared with the Screening Visit.

- 7a. Participant has had no change in corticosteroid dose during the Screening Period and no change in corticosteroid dose is anticipated to occur during the 12-week Main Treatment Period.

- 8a. Participant has had no change in immunosuppressive therapy, including dose, during the Screening Period and no change in immunosuppressive therapy is anticipated to occur during the 12-week Main Treatment Period.

- 9a. Participant has a record of vaccination with at least 1 dose of a quadrivalent meningococcal vaccine and meningococcal serotype B vaccine at least 14 days prior to the first dose of ZLP if not vaccinated within 3 years prior to the start of study medication.

Participants who initiate study medication less than 2 weeks after receiving a meningococcal vaccine must receive treatment with appropriate prophylactic antibiotics (eg, penicillin V 500mg twice daily, third generation cephalosporin) until at least 2 weeks after the initial dose of vaccine(s). The use of fluoroquinolone or macrolide antibiotics is not recommended due to the potential for exacerbation of MG.

A booster vaccination should also be administered, as clinically indicated, to participants who have been previously vaccinated against *N. meningitidis* in order to be eligible for inclusion in this study. Participants also must agree to receive a booster vaccination during the study according to the most current relevant guideline (ie, Advisory Committee on Immunization Practices, United States).

## Sex

### 10a. Male and/or female

- A male participant is recommended to agree to use contraception as detailed in Appendix 4 (Section 10.4) of this protocol during the study and for at least 40 days (5 half-lives) after the last dose of study medication, and refrain from donating sperm during this period.
- A female participant is eligible to participate if she is not pregnant (see Appendix 4 [Section 10.4]), not breastfeeding, and at least one of the following conditions applies:
  - Not a woman of childbearing potential (WOCBP) as defined in Appendix 4 (Section 10.4)
  - OR
  - A WOCBP who agrees to follow the contraceptive guidance in Appendix 4 (Section 10.4) during the study and for at least 40 days (5 half-lives) after the last dose of study medication.

## Informed consent

### 11. Participant is capable of giving signed informed consent as described in Appendix 1 (Section 10.1), which includes compliance with the requirements and restrictions listed in the ICF and in this protocol.

## 5.2 Exclusion criteria

Participants are excluded from the study if any of the following criteria apply:

### Medical conditions

1. Participant has any medical or psychiatric condition that, in the opinion of the Investigator, could jeopardize or would compromise the participant's ability to participate in this study.
2. Participant has a known hypersensitivity to any components of the study medication as stated in this protocol.
- 3a. Participant has had a thymectomy within 6 months prior to Baseline or has one scheduled to occur during the 12-week Main Treatment Period.
4. Participant has a history of meningococcal disease.
5. Participant has or has had a current or recent systemic infection within 2 weeks prior to Baseline or an infection requiring IV antibiotics within 4 weeks prior to Baseline.
6. Participant has active malignancy (except curatively resected squamous or basal cell carcinoma of the skin) requiring surgery, chemotherapy, or radiation within the prior 12 months (participants with a history of malignancy who have undergone curative resection

---

or otherwise not requiring treatment for at least 12 months prior to Screening with no detectable recurrence are allowed).

7. Participant has a lifetime history of suicide attempt (including an actual attempt, interrupted attempt, or aborted attempt), or has had suicidal ideation with at least some intent to act in the past 6 months as indicated by a positive response ("Yes") to either question 4 or question 5 of the "Screening/Baseline" version of the C-SSRS at Screening.
8. Participant has alanine transaminase (ALT), aspartate aminotransferase (AST), or alkaline phosphatase (ALP)  $>2.5 \times$  upper limit of normal (ULN).
9. Participant has bilirubin  $>1.5 \times$ ULN (isolated bilirubin  $>1.5 \times$ ULN is acceptable if bilirubin is fractionated and direct bilirubin  $<35\%$ ).
10. Participant has current unstable liver or biliary disease per Investigator assessment defined by the presence of ascites, encephalopathy, coagulopathy, hypoalbuminemia, esophageal or gastric varices, persistent jaundice, or cirrhosis.

NOTE: Stable chronic liver disease (including Gilbert's syndrome, asymptomatic gallstones, and chronic stable hepatitis B or C) is acceptable if the participant otherwise meets entry criteria.

For study participants with a baseline result  $>$ ULN for ALT, AST, ALP, or total bilirubin, a baseline diagnosis and/or the cause of any clinically meaningful elevation must be understood and recorded in the electronic case report form (eCRF).

If a study participant has  $>$ ULN ALT, AST, or ALP that does not meet the exclusion limit at Screening, repeat the tests, if possible, prior to dosing to ensure there is no further ongoing clinically relevant increase. In case of a clinically relevant increase, inclusion of the study participant must be discussed with the Medical Monitor.

Tests that result in ALT, AST, or ALP up to 25% above the exclusion limit may be repeated once for confirmation.

11. QTc interval  $>450$ msec for male participants, QTc  $>470$ msec for female participants, or QTc  $>480$  msec in participants with bundle branch block.

NOTE: The QTc is the QT interval corrected for heart rate according to Fridericia's formula (QTcF). It is either machine read or manually overread.

#### **Prior/Concomitant therapy**

- 12a. Participant has had recent surgery requiring general anesthesia within 2 weeks prior to Screening or is expected to have surgery requiring general anesthesia during the 12-week Main Treatment Period.
13. Participant has received a treatment with an experimental drug within 30 days or 5 half-lives of the experimental drug (whichever is longer) prior to Baseline.
- 14a. Participant has received treatment with rituximab within 6 months prior to Baseline or treatment is planned to occur during the study.
15. Participant has received treatment with IVIG, SC immunoglobulin, or PLEX 4 weeks prior to Baseline or participant is on chronic IVIG, SC immunoglobulin, or PLEX.

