d For study participants who require rescue therapy (see Section 6.5.4), a Rescue Therapy Visit should be conducted prior to the initiation of rescue therapy. If the Rescue Therapy Visit coincides with a regularly scheduled study visit, then overlapping study procedures do not need to be duplicated. The study participant will continue ZLP treatment while undergoing rescue therapy if it is considered by the Investigator to be in his/her best interest.

e In circumstances where COVID-19 disruptions lead to a study participant being unable to return for Day 1 after 14 or 56 days of the Screening Period, respectively, additional days may be included in the Screening Period. Contact with the Medical Monitor is requested in such situations.

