## 4 STUDY DESIGN

### 4.1 Overall design

MG0017 is a Phase 3b, multicenter, open-label, single-arm study to evaluate the safety, tolerability, and efficacy of ZLP in study participants with gMG switching from their current IV C5 inhibitor to SC ZLP.

To be eligible to participate in this study, participants must be adults ( $\geq 18$  years of age) with a documented diagnosis of gMG (Myasthenia Gravis Foundation of America [MGFA] Class II-IVa), currently receiving an IV C5 inhibitor approved for the treatment of gMG for at least 3 months (for eculizumab) or 4 months (for ravulizumab) prior to Screening (with the last dose being administered at the Screening Visit  $\pm 3$  days), considered to have a clinically stable disease as per the Investigator's judgment prior to Screening, and willing to switch from their current IV C5 inhibitor to SC ZLP.

The planned enrollment is 20 study participants in the US.

The study includes a 2-week or 8-week Screening Period (for participants receiving eculizumab or ravulizumab, respectively), a 12-week Main Treatment Period, and an optional Extension Treatment Period. A SFU Visit should be performed 40 days ( $\pm 7$  days) after the last dose of study medication (Section 6.8, Section 1.2).

The Screening Visit should be scheduled to coincide with the regularly scheduled study participant's IV C5 inhibitor administration ( $\pm 3$  days). Up to and including the time of the Screening Visit, study participants will continue to receive their IV C5 inhibitor at the recommended dose regimen. The last regularly scheduled IV C5 inhibitor administration cannot occur beyond Day -14 ( $\pm 3$  days) of the Screening Period for study participants receiving eculizumab or beyond Day -56 ( $\pm 3$  days) of the Screening Period for study participants receiving ravulizumab to ensure approximately a 2-week or 8-week interval between the last regularly scheduled IV C5 inhibitor administration (administered at the Screening Visit  $\pm 3$  days) and the first SC ZLP administration at the Baseline Visit, respectively.

At the end of the Screening Period and in case of no more than a 2-point change in study participants' MG-ADL score compared to the Screening Visit, study participants will enter the Main Treatment Period and will switch to SC ZLP (IV C5 inhibitor should not be administered after the Screening Visit). On Day 1, study participants will receive ZLP 0.3mg/kg administered

---

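### Exclusion 12a leaves the Screening Period uncovered: surgery under general anaesthesia between Screening and Day 1 falls in neither of its two intervals

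*Protocol*

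**What the plan says.** Exclusion 12a (Protocol section 5.2) has two limbs. The backward limb applies when "Participant has had recent surgery requiring general anesthesia within 2 weeks prior to Screening". The forward limb continues "or is expected to have surgery requiring general anesthesia during the 12-week Main Treatment Period".

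The Main Treatment Period starts on Day 1. Section 4.1 and Table 1-2 put the Screening Visit at Day -14 for participants coming from eculizumab and Day -56 for those coming from ravulizumab, with a 3-day window. For COVID-19 disruption, a footnote to Table 1-2 adds that "additional days may be included in the Screening Period", with no stated limit.

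Several other exclusions in section 5.2 count back from Baseline. Criterion 3a reads "Participant has had a thymectomy within 6 months prior to Baseline". Criterion 5 covers "current or recent systemic infection within 2 weeks prior to Baseline". Criteria 13 (experimental drug), 14a (rituximab) and 15 (IVIG, SC immunoglobulin, PLEX) are also anchored to Baseline.

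**The concern.** The two limbs of 12a do not meet. The stretch between them is the one closest to the first dose, so the criterion screens out an older operation and admits a more recent one. That ordering is hard to see as intended, given that the criteria on thymectomy, infection and recent treatment run to Baseline.

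The study has no control arm. If a participant enters while still affected by an operation, recovery between Baseline and Week 12 is read as maintained disease control on zilucoplan and favours the noninferiority conclusion on MG-ADL. The planned summaries are not set up to separate this out.

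**Working it through.** **1. Intervals named in 12a, on the study-day scale (nominal visit days).**

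| | Eculizumab | Ravulizumab |
|---|---|---|
| Screening Visit | Day -14 | Day -56 |
| Backward limb (2 weeks before Screening) | Day -28 to -14 | Day -70 to -56 |
| Forward limb | Day 1 to Week 12 | Day 1 to Week 12 |
| In neither limb | about 14 days | about 56 days |

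With the 3-day Screening window the gap is 14 - 3 = 11 to 14 + 3 = 17 days for eculizumab, and 56 - 3 = 53 to 56 + 3 = 59 days for ravulizumab. It is longer if Screening is extended.

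**2. Test cases.**
- Ravulizumab, surgery 9 weeks before Day 1: Day -63, inside Day -70 to -56, so excluded.
- Ravulizumab, surgery 1 week before Day 1: Day -7, in neither limb, so eligible under 12a.
- Eculizumab, surgery 3 weeks before Day 1: Day -21, inside Day -28 to -14, so excluded.
- Eculizumab, surgery 1 week before Day 1: Day -7, in neither limb, so eligible under 12a.

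Table 1-2 schedules a second eligibility check at Baseline, but that check applies the same two limbs and gives the same answers.

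**3. Would re-anchoring alone close the gap?** A 2-week look-back from Baseline covers Day -14 to Day 1. Uncovered Screening days would be 14 - 14 = 0 (eculizumab) and 56 - 14 = 42 (ravulizumab). The present cover before Screening would also be lost. Swapping the anchor therefore closes the gap for one prior drug only.

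**4. Scale against the plan's own figures.** Protocol section 9.8 assumes SD 3, true change 0, margin 2, N = 20 and 1-sided alpha 0.025.
- Standard error = 3/√20 = 0.671.
- Noncentrality = 2/0.671 = 2.98 on 19 df, giving power of 80.7%. This reproduces the stated figure of about 80%.
- Largest observed mean change that passes = 2 - 2.093 × 0.671 = 0.596.
- Assumption: one participant recovers 1 to 2 MG-ADL points after Baseline. The mean moves by 1/20 = 0.05 to 2/20 = 0.10, which is 0.07 to 0.15 of the standard error.

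The simple mean stands in here for the MMRM least-squares mean that SAP section 5.3.1.1.2 will test. The gap itself depends on none of these figures.

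**The case against.** The strongest reply is that other criteria already catch most of the participants who matter:

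- Exclusion 3a covers thymectomy, the operation most specific to this disease, up to Baseline.
- Exclusion 5 removes recent systemic infection, and infection needing IV antibiotics within 4 weeks before Baseline.
- Exclusion 6 deals with active malignancy requiring surgery.
- Exclusion 1 lets the investigator exclude on any medical condition judged to compromise participation.
- Inclusion 6 allows no more than a 2-point MG-ADL change between Screening and Baseline, so a participant who deteriorates by 3 or more points after an operation does not enter.

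All of this stands, and it narrows the gap. It does not close it. None of these criteria names general-anaesthesia surgery during Screening, and a participant who worsened by up to 2 points may still enter.

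It is also fair to say that anchoring to Screening is not peculiar to 12a. Inclusion 2a and the treatment-free time in exclusion 6 count back from Screening, and exclusion 7 is assessed there. The anchor alone is therefore not the fault. The fault is that 12a resumes only on Day 1 and skips the days between.

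**Conclusion.** The point holds as a minor fault in the wording of one exclusion criterion. About 14 days (eculizumab) or 56 days (ravulizumab) before Day 1 are outside 12a. The day counts rest on the nominal visit schedule. The 0.05 to 0.10 shift rests on an assumed recovery of 1 to 2 points in one participant.

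Three stronger readings are tempting, and the documents do not support them.

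- A reader might infer that the stability criteria have the same defect, since 7a says "Participant has had no change in corticosteroid dose during the Screening Period" and 8a says "Participant has had no change in immunosuppressive therapy, including dose, during the Screening Period". Those windows do run up to Day 1. Their lengths differ (14 against 56 days) because the Screening Period follows the prior drug's infusion interval. The documents set no minimum that the shorter window breaches, and 2a separately requires disease that the investigator judges stable. A uniform window would be a preference.
- A reader might scale the shift up to several participants and set it against the 0.596 threshold. No rate of surgery is given anywhere, so the effect on the MG-ADL mean cannot be quantified.
- A reader might infer that perioperative events inflate the primary TEAE count generally. Appendix 3 says a procedure is not itself an AE. SAP section 5.4.2.1 does not count events that start before the first dose; Protocol section 9.4.1 would add pre-existing events that worsen after it. Only events that start or worsen after the first dose could enter.

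**What to change.** Reconcile 12a with 3a, 5, 13, 14a and 15 so that its cover is continuous up to Baseline. One way is to keep the existing look-back and add surgery during the Screening Period as a further interval. Replacing Screening with Baseline is not enough on its own, because with a 2-week look-back it would leave about 42 days open for ravulizumab users. How far back the criterion should reach is for the sponsor to decide.

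The cost is one phrase in a protocol amendment, and an occasional participant who is delayed or rescreened. If enrolment has closed, a by-participant listing of any general-anaesthesia surgery between the Screening Visit and Day 1 would let readers see whether the gap was ever used.

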### **Prior/Concurrent clinical study experience**

16. Participant has previously participated in this study or participant has previously been assigned to treatment in a study of the medication under investigation in this study.
17. Participant has participated in another study of an investigational study medication (and/or an investigational device) within the previous 30 days or is currently participating in another study of an investigational study medication (and/or an investigational device).

### **Diagnostic assessments**

18. Participant has known positive serology for muscle-specific kinase.

### **5.3 Lifestyle restrictions**

There are no lifestyle restrictions during the study.

### **5.4 Screen failures**

Screen failures are defined as study participants who consent to participate in the clinical study but are not subsequently entered in the study. A minimal set of screen failure information is required to ensure transparent reporting of screen failure participants to meet the Consolidated Standards of Reporting Trials publishing requirements and to respond to queries from regulatory authorities. Minimal information includes demography, screen failure details, eligibility criteria, and any serious adverse event (SAE).

In case of screen failure, the study participant can be rescreened twice following discussion with the UCB Medical Monitor and/or Study Physician.

## **6 STUDY TREATMENTS**

Study treatment is defined as any investigational treatment(s), marketed product(s), placebo, or medical device(s) intended to be administered to a study participant according to the study protocol.

Up to and including the time of the Screening Visit, study participants will continue to receive their IV C5 inhibitor at the recommended dose regimen. Study treatment (ZLP) will be administered during the Main Treatment and Extension Treatment Periods.

### **6.1 Treatments administered**

The treatment administered in MG0017 is presented in [Table 6-1](#).

**Table 6–1: Treatment administered**

Arm name	Zilucoplan
Intervention name	Zilucoplan
Type	Drug
Dose formulation	Pre-filled syringe
Unit dose strength(s)	16.6mg in 0.416mL 23.0mg in 0.574mL 32.4mg in 0.810mL
Dosage level	0.3mg/kg/day
Route of administration	Subcutaneous injection
Use	Experimental
IMP	IMP
Sourcing	Provided centrally by the Sponsor
Packaging and labeling	Study medication will be provided in kits containing 7 prefilled syringes. Each syringe and kit will be labeled as required per country requirement.
Excipients	
Former names	RA101495

IMP=investigational medicinal product; NIMP=noninvestigational medicinal product

Zilucoplan 0.3mg/kg/day administered SC is the selected dose for this study. As in other ZLP studies, the dose presentation will be selected using the following weight brackets ([Table 6–2](#)).

